Individuals who meet the inclusion criteria will be scheduled for Visit 0. Study enrollment occurs when a participant arrives at Visit 0. The first 60 participants will complete Visits 1 and 2, while the remaining participants will only complete Visit 2. Visit 1 occurs at least 3 weeks after Visit 0 and Visit 2 occurs at least 3 weeks after Visit 1.

Visit 0:

The following procedures and assessments will be conducted at Visit 0:

1. Obtain informed consent
2. Perform urine screening for toxicology (random selection)
3. Urine pregnancy test (females only)
4. Administer health history form and review eligibility criteria, complete and sign eligibility form
5. Administer questionnaires (STAI-T, STAI-S, SCQ, BDI, EHI, BIS-11)
6. Pain scale training on COVAS
7. Quantitative Sensory Testing (QST) thermal threshold/supra-threshold testing (see below for details)
8. Offset analgesia test (see below for details)
9. Administer post-pain questionnaires (PCS, SFMPQ)
10. Ice pack application – total of 5 minutes or until pain = 0 for 60 seconds
11. Capsaicin application and incubation
12. Brush allodynia test and flare mapping
13. Ice pack application – total of 5 minutes or until pain = 0 for 60 seconds
14. Payment form completion
15. Schedule Visit 1

Visit 1:

The following procedures and assessments will be conducted at Visit 1:

1. Perform urine screening for toxicology (random selection)
2. Urine pregnancy test (females only)
3. Review eligibility criteria, complete and sign eligibility form

Date: 6/6/2018

Principal Investigator: [name].

Application Number: HP-00064214

4. Administer questionnaires (STAI-T, STAI-S, SCQ, BDI, EHI, BIS-11)
5. Pain scale training on COVAS
6. EEG cap setup
7. Quantitative Sensory Testing (QST) thermal threshold/supra-threshold testing (see below for details)
8. Offset analgesia test (see below for details)
9. Ice pack application – total of 5 minutes or until pain = 0 for 60 seconds
10. Resting state EEG runs (acute series):
 - a. 1 minute eyes open resting state
 - b. 1 minute eyes closed resting state
 - c. Baseline-acute resting state – 5 minutes (baseline thermode on)
 - d. Painful-acute resting state – 5 minutes
 - e. Administer post-pain questionnaires (PCS, SFMPQ)
 - f. Ice pack application – total of 5 minutes or until pain = 0 for 60 seconds (no EEG recorded)
 - g. Acute-return baseline resting state – 5 minutes
11. 5 minute break
12. Resting state EEG runs (chronic series):

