with at least 30 seconds between trials, and the thermode is moved to a different position on the forearm/face/neck for each trial. The T1 and T2 durations for the three trials are: 4s/5s, 7s/4s, 5s/6s. We will subsequently test for offset analgesia at each body site while a second stimulus is simultaneously applied to another body site. This will be done for the following combinations of body sites: arm/face, left arm/right arm. Participants will be instructed to rate the pain intensity at one of the two sites using the COVAS.

Test for Brush Allodynia. This test is performed last, after incubation at V0 and after rekindle at V1 and V2. The capsaicin cream and film cover are removed, and the arm area is cleaned with alcohol and the original 1 inch square site is marked. The area of secondary hyperalgesia on the participant's arm is measured with a foam paintbrush dragged at 1 cm per second along four linear paths arranged vertically and horizontally around the marked capsaicin site. Brush stimulation from each direction is started outside the hyperalgesic area, and continued towards the marked square until the participant reports a change in sensation ('burning', 'tenderness', 'pain'). The border is marked on the skin with a marker from each direction. Finally the flare outside the capsaicin site is traced on transparency paper.

EEG

The EEG session will last about 2 hours and will include the following runs: 1 minute open eyes resting state, 1 minute closed eyes resting state, 5 minutes run of baseline-acute resting state, 5 minute run of acute-painful resting state, 5 minute run of acute-return baseline resting state, 15 minute run of capsaicin cream incubation, , 5 minute run of chronic-painful resting state, and 5 minute run of chronic-return baseline resting state, 5 minute run of chronic-painful resting state (rekindle).

Urine Screening

Urine screening will be decided randomly, by allowing the participant to choose 1 of 10 envelopes that s/he opens to reveal his or her assignment. 9 of the envelopes contain a paper that says 'No' to indicate no urine test and 1 envelope contains a paper that says 'Yes' to indicate a urine test will be conducted. Urine samples will be collected and immediately discarded after screening for drug toxicology. A urine sample for toxicology screening testing will be collected in a urine collection cup. The toxicology screening will be performed using Instant-View 12 Panel Drug Tests.

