Barratt Impulsiveness Scale (BIS-11). This 30-item questionnaire measures impulsive personality traits by self-report. The BIS score is determined using first order factors (attention, motor, self-control, cognitive complexity, perseverance, cognitive instability) and second order factors (attentional, motor, nonplanning) (Patton et al., 1995).

Date: 6/6/2018

Principal Investigator: [name].

Application Number: HP-00064214

11. Risks and benefits

Research-related risk, likelihood/seriousness of the risk, and provisions for minimizing the risk

Some of the heat stimuli will be painful to participants. Participants will be able to stop the stimulation (the heat or cold on the skin) at any time if participants find it too uncomfortable. The stimulation equipment is designed not to exceed safe temperatures, but there is a small chance of short-lasting tissue injury such as redness, tenderness, and/or in very rare cases minor blistering at the site where heat has been applied. Any effects should go away within 24 hours. No reports of serious injuries from this stimulator have been made to the manufacturers or the FDA. (The FDA is the government agency that oversees the safety of drugs, vaccines, and medical devices.)

During each visit participants will be asked to endure controlled experimental pain. For the temporary pain, participants will be exposed to a hot temperature for a total of 5 minutes. For the capsaicin pain, participants will be exposed to capsaicin for up to 40 minutes. Each type of pain will only occur once per visit and will be well controlled. If participants want to stop this portion of the experiment at any time we will stop the pain with no prejudice. Participants will be reminded they may elect to end the experiment at any time at each session. Any residual pain can be eliminated by applying a cold wet cloth.

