From wearing the EEG cap, participants may experience slight sensations and irritation as the scalp is lightly rubbed at the recording sites. There is some risk that the skin may be broken during the EEG cap preparation, however this is rare in our lab. Also, a small number of people may be allergic to the conducting gel and/or adhesive used to attach the other sensors on the skin, but this is rare. Please let us know if participants are experiencing irritation around sensor placement areas. Lastly, if participants experience a temporary reddening of the skin around any of the sensor sites, this typically goes away within an hour or so.

Participants may feel at unease when reading or responding to personal questions. Participants can refuse to answer any question and stop at any time.

There is a very small risk for breach of confidentiality of the information that participants provide for this study. We will do the most we can to keep their information secure and confidential. Loss of confidentiality will be minimized by storing data in a locked cabinet and on password-protected computers.

Participants will be asked to contact a study team member to report unanticipated events or potential adverse events (see Data and safety monitoring plan).

Potential direct benefit(s) to participants

There is no direct benefit to participants.

Importance of the knowledge expected to result from the study

The study will provide critical knowledge about the brain mechanisms of pain. We study this by stimulating the arm with thermal stimuli and examining EEG activity before and during the experience of pain. This could lead to an objective test of sensitivity to pain and could guide preventive and therapeutic approaches to chronic pain in future work.

Date: 6/6/2018

Principal Investigator: [name].

Application Number: HP-00064214

How the potential risks to participants are reasonable in relationship to the potential benefits

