There are minimal risks to the subject, but potentially great gains for the pain research community from the outcomes of the present study. The potential risks to participants associated with sensory testing and EEG are minimal. The thermal stimulation device delivers temperatures that produce the perception of pain without creating any lasting effects such as a burn to the skin, unlike situations commonly encountered in daily life (burning of the mouth on hot coffee or pizza, burning a hand on a stove). The benefits of identifying brain mechanisms associated with different types of pain are potentially very great for the pain research community, as the information may lead to developing novel treatments for chronic pain and a biomarker for pain sensitivity.

Alternatives to participation in this study

Participation is voluntary and the alternative to participating is to not participate.

12. Withdrawal or Removal

Subjects are free to withdraw from participation in the study at any time upon request, and the investigator may withdraw a subject from participation for any of the following reasons:

- Withdrawal of consent.
- Subject noncompliance with the protocol that results in inability to assess primary outcomes.
- Any event, condition, or situation that would make continued participation in the study not in the best interest of the subject, as determined by the investigator.
- Investigator discretion.

Whether a participant has completed all the requirements of the study or decides to terminate his or her participation before all the requirements are met, we ask nothing further of that participant. If the participant has completed a partial session, the data collected in that time may be used in the group analyses.

13. Privacy

Screening, consent, and testing will be done in private rooms. Study team members who have access to participant names will not talk about participants using names, whether in private or public. When contacting participants by phone, information about the study will only be given directly to the participant.

Potential participants will receive research information from recruitment posters around the Baltimore area and university campuses, including UMB, UMMS, UMBC, and Johns Hopkins. Further information will be given via telephone when the potential participant calls the phone number on the recruitment letter or poster.

14. Confidentiality

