Participants will be numerically coded upon enrollment. Only the team members directly involved with the participants will have access to their names, and once a participant has completed the study, only numerical codes will be used. The original list with the codes and names will be securely locked.

Date: 6/6/2018

Principal Investigator: [name].

Application Number: HP-00064214

Identifiable data will be kept in the PI's office. Coded data will be kept on a central server that can only be accessed by research team members (password protected).

Identifiable data will be kept in a locked filing cabinet.

The PI will have access to identifiable data. Only research team members will have access to coded data.

15. Data and safety monitoring plan

Data Safety Monitoring by the PI and reported to the IRB semi-annually.

The PI will take note of any unexpected risks or harm to the participants and report them to the IRB and the sponsor, Purdue Pharma LP.

Data to be reviewed include enrollment, adverse events, unanticipated events, and preliminary analyses.

Participants will be asked to contact a study team member to report unanticipated events or potential adverse events.

16. Payment

For their time, participants will be compensated \$25 for the eligibility screening visit and \$75 per EEG visit. Payments will be made by check.

17. Sample size calculation

The target sample size for this study is 120 healthy male and female subjects. This number is based on our preliminary data and accounts for variability in the response to capsaicin (about 10% of people do not react to topical capsaicin). Additionally, this sample size is sufficiently powered to capture a moderately size relationship ($r > .3$) between pain and peak alpha frequency, according to a correlation power analysis with a Type I error rate of .05 and a Type II error rate of .2. The sample size is also sufficient for performing multivariate analyses, which will allow us to develop data-driven algorithms for pain sensitivity.

18. Data analysis plan

Data Analysis Approach

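### No visit schedules an adverse-event question and no contact follows a visit, so skin effects after departure reach the safety review only if the participant volunteers them

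*Combined protocol and SAP*

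**What the plan says.** Section 11 (Risks and benefits) describes the expected harm from the heat stimulus. It names redness and tenderness, and "in very rare cases minor blistering at the site where heat has been applied". It then gives a time course: "Any effects should go away within 24 hours".

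Sections 11 and 15 (Data and safety monitoring plan) give the same route for collecting events: "Participants will be asked to contact a study team member to report unanticipated events or potential adverse events". Section 15 adds a second route: "The PI will take note of any unexpected risks or harm to the participants and report them to the IRB and the sponsor". It names adverse events among the data to be reviewed, with semi-annual reporting to the IRB. For the EEG cap, Section 11 has a further invitation to speak up: "Please let us know if participants are experiencing irritation around sensor placement areas".

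Section 9 (Detailed procedures) numbers the steps of each visit. None is an adverse-event question, and no contact after a visit is listed. Staff do handle the stimulated skin when they apply ice, remove the capsaicin and map the response: "Finally the flare outside the capsaicin site is traced on transparency paper". The spacing is wide: "Visit 1 occurs at least 3 weeks after Visit 0 and Visit 2 occurs at least 3 weeks after Visit 1".

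Section 12 (Withdrawal or Removal) says of anyone who has finished or stopped: "we ask nothing further of that participant".

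**The concern.** The protocol predicts effects on a 24-hour scale, and participants go home well before 24 hours have passed. From then on, the plan depends on the participant deciding that a red or tender patch is worth reporting. Mild effects of the kind the protocol has already told people to expect are the ones least likely to prompt a call or message.

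At stake is the adverse-event count in the semi-annual review. If few events are volunteered, that report cannot separate few events from few reports. Section 11 justifies participation by minimal risk without lasting effects, so the study should be able to describe what happened after its own sessions.

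**Working it through.** The plan states no figure on this point, so there is none to reproduce. The check is a reading of the procedure lists, a count of exposures and a labelled illustration.

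**1. What each visit asks (Section 9).**
- Visit 0: consent, urine tests, health history and eligibility, questionnaires, thermal testing, capsaicin, brush test and flare mapping, ice, payment, scheduling. No event question.
- Visits 1 and 2: step 3 is an eligibility review. The last listed steps are capsaicin removal with brush test and flare mapping, cap removal and payment, plus scheduling at Visit 1. No event question at the start or the end.
- After any visit: nothing listed.

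Events visible in session can be noted. Events that begin or persist after departure have no scheduled enquiry.

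**2. Exposure visits.** Inputs: 120 enrolled (Section 8). The first 60 attend Visits 0, 1 and 2, and the remaining 60 attend Visits 0 and 2 (Section 9). About 10% do not react to capsaicin (Section 17) and so are not eligible to continue after Visit 0 (Section 4).
- Maximum: 120 + 60 + 120 = 300.
- With 10% ending at Visit 0, spread evenly over both halves: 120 + 54 + 108 = 282.

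**3. Coverage of the 24 hours.**
- Each participant has one last visit: 120 of 300 (40%), or 120 of 282 (43%), have no later scheduled contact.
- The other 300 − 120 = 180 (or 282 − 120 = 162) are followed by a visit at least 21 days later that lists no event question.
- Exposure visits with a scheduled enquiry covering the next 24 hours: 0.

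**4. Illustration only.** The documents give no event rate *p* and no share *q* of events that get recorded. Both are assumed here, and visits are treated as independent although they come from at most 120 people.

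If no event is recorded in 300 visits, the one-sided 95% upper bound on the recorded rate is 1 − 0.05^(1/300) = 0.99%. Dividing by *q* gives a bound on the true rate of 1.0% at *q* = 1, 2.0% at *q* = 0.5 and 4.0% at *q* = 0.25.

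The chance of recording nothing is (1 − *pq*)^300:

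| assumed *p* per visit | *q* = 1 | *q* = 0.5 | *q* = 0.25 |
|---|---|---|---|
| 0.5% | 22.2% | 47.2% | 68.7% |
| 1% | 4.9% | 22.2% | 47.2% |
| 2% | 0.2% | 4.9% | 22.2% |
| 5% | below 0.1% | 0.1% | 2.3% |

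This shows how a blank record loses meaning as reporting falls. It does not estimate what this study would miss.

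**The case against.** The strongest reply is that the plan is less passive than it looks, and much of that reply stands.

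- A reader might infer that events are captured only when a participant phones in. The text does not support that. It says contact, by any means, and Section 15 separately has the investigator note unexpected risks or harm. That second route has no form or timing, and the word unexpected may leave out the anticipated skin effects, but it exists.
- Staff see the arm at every visit during ice application, capsaicin removal and flare tracing. These are study procedures, yet visible injury would be in front of them. The gap is confined to what arises or persists after departure.
- A reader might infer that repeat exposure of the forearm would proceed on the strength of a low event count. Nothing in the documents links the two. Eligibility is reviewed again at Visits 1 and 2, and the Section 7 criteria require freedom from acute pain and let the investigator exclude anyone at increased risk.
- A reader might take the Section 12 sentence as a rule against safety follow-up. It sits in the withdrawal provisions and most naturally means that a departing participant owes nothing more.
- The 24-hour statement is an expectation in a risk description. It is not an endpoint, and both aims concern EEG alpha activity.
- The consent pages, eligibility form and study flow form are not available here, so an unlisted prompt cannot be excluded.

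What remains is that the numbered steps contain no event question and no later contact, while adverse events are a review item.

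**Conclusion.** The point holds in a limited form and is minor. As listed, no visit includes a solicited adverse-event enquiry, and none of the at most 300 exposure visits has one covering the following 24 hours; 120 have no later scheduled contact of any kind. Effects after departure enter the semi-annual review only if volunteered, so the count is liable to be low.

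It would go too far to say that the review will under-count, or by how much. That needs an event rate and a reporting share, and the documents give neither; the 2% and 4% bounds rest wholly on assumed shares. The conclusion also assumes that the unseen forms add no event question.

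**What to change.** 1. Add one standard adverse-event question, with a recorded look at the stimulated sites, before departure at every visit. Repeat it within the existing eligibility review (step 3) of Visits 1 and 2.
2. Send one brief text, e-mail or phone contact shortly after the 24-hour window following each visit, and record the answers. Contact after the final visit alone would leave up to 180 earlier exposures to recall at three weeks or more.
3. State in Section 12 that this contact is permitted, and in Section 14 that the identifier list is used for it. This is needed because Section 8 has screening forms destroyed on enrolment and Section 14 restricts use to codes after completion. In the semi-annual review, report solicited and volunteered events separately, per exposure visit.

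The cost is up to about 300 short contacts by existing staff, a minor amendment with consent wording, and a few more minor events on record. If item 2 is judged too burdensome, item 1 alone is still worthwhile. No stimulus, schedule or stopping rule changes.

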Data preprocessing for all resting state scans will proceed as follows: data will be re-referenced to the average of the two ear electrodes, band-pass filtered, removed of obvious non-brain (i.e. movement) artifacts, and epoched into 4 second segments. Following preprocessing, a fast fourier transform will be applied to each epoch. The resulting spectral information will then be averaged across epochs. This spectral information will then be exported to Matlab where it will be analyzed with custom scripts developed in our laboratory. Activity in the alpha frequency band (8-12hz) will serve as the primary frequency band of interest.

Interim Data Analysis

Following acquisition of five full data sets, preliminary analyses will occur to assess the primary study outcomes and provide an opportunity to modify the protocol if necessary.

Aim 1. To determine how the experience of innocuous and noxious stimulation affects alpha activity.

Date: 6/6/2018

Principal Investigator: [name].

Application Number: HP-00064214

First, to identify the potential mechanisms that may drive modulations of alpha frequency under painful conditions, we will compare both the acute pain and neuropathic-like pain state scans against the most temporally proximate innocuous state scans. Each pain state will be compared to the baseline scan directly preceding it, and the differences between acute pain and warm and neuropathic-like pain and warm will be compared.

Second, we will compare the spectral characteristics of acute pain and neuropathic-like pain in the alpha frequency band and determine the ability of alpha frequency measures distinguish these two pain states. Each pain state will be compared to the baseline scan directly preceding it, and the differences between acute pain and warm and neuropathic-like pain and warm will be compared.

Aim 2. To assess the test-retest reliability of the alpha frequency as an objective measure of pain in two different experimental pain states (acute and neuropathic-like).

Here, we will identify the degree to which alpha frequency under various pain states remains constant across this time. This will be accomplished by comparing the resting states, and the differences between them, across testing sessions. If alpha frequency observations remain stable, within an individual, across testing sessions, this will provide important evidence that alpha frequency, and how it shifts, may represent an individually based characteristic or biomarker.

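### EEG artifact removal has no objective criterion and no masking to condition, so it could bias the Aim 1 pain-minus-baseline difference by an amount that the documents do not allow one to compute

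*Combined protocol and SAP*

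**What the plan says.** Section 18, Data Analysis Approach, sets a single pipeline ("Data preprocessing for all resting state scans will proceed as follows"). After re-referencing and filtering, the data are "removed of obvious non-brain (i.e. movement) artifacts, and epoched into 4 second segments". A Fourier transform follows, and then: "The resulting spectral information will then be averaged across epochs". The output is "analyzed with custom scripts developed in our laboratory".

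For Aim 1 the contrast is within subject: "Each pain state will be compared to the baseline scan directly preceding it".

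Outcome data are looked at while the study runs. Section 18, Interim Data Analysis: "Following acquisition of five full data sets, preliminary analyses will occur to assess the primary study outcomes", with the option of changing the protocol. Section 15: "Data Safety Monitoring by the PI and reported to the IRB semi-annually", and "Data to be reviewed include enrollment, adverse events, unanticipated events, and preliminary analyses".

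The only coding described is of participant identity (Section 14). Masking to scan condition, visit or pain rating is not mentioned in any section.

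**The concern.** Whether an artifact is *obvious* is a judgement. Section 18 gives no amplitude limit, algorithm, number of raters, minimum amount of retained data, report of removal by condition, or sensitivity analysis. The judgement is made before the spectra are averaged, so whatever is kept determines the alpha estimate.

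Section 6 gives the team a direction to expect in each pain state. Higher peak alpha frequency is reported to go with more pain under acute heat, and the laboratory's own capsaicin data showed the opposite relation. A step with no criterion and no masking is most exposed when the expected result is known and early results are being examined.

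At stake is the Aim 1 difference between each pain scan and its baseline. Removal that differs between the two scans, and is related to alpha frequency, enters that difference directly. Recruiting more participants does not reduce it.

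**Working it through.** **1. Is there a figure in the plan to reproduce?** Not on this point: the documents give no rejection rate, epoch-level SD or SD of the paired difference. The one computed quantity is the sample size in Section 17 (120, for r > 0.3, Type I error 0.05, Type II error 0.2). Fisher's z gives n = ((1.960 + 0.842)/atanh 0.3)² + 3 = 84.9, so 85 two-sided, and 85/0.9 = 95 after rounding up for the stated 10% who do not react to capsaicin. The plan's 120 exceeds this. It is said to rest also on preliminary data that are not shown. Sample size is not in dispute here.

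**2. Data per scan.** Section 4 gives five minutes per scan, with acute pain as five one-minute scans. In 4-second epochs that is 300/4 = 75, or 5 × (60/4) = 75 for the acute condition. Removing 5%, 10% or 20% takes out about 4, 7.5 or 15 epochs.

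**3. Upper bound on the shift.** Suppose epoch values are normal and a fraction f is removed wholly from one tail in one of the two scans. That scan's mean moves by φ(z)/(1 − f) epoch-level SDs, where z cuts off the tail f. If removal instead follows a score that correlates ρ with epoch alpha, multiply by ρ.

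| f | ρ = 1 (upper bound) | ρ = 0.3 | ρ = 0 |
|---|---|---|---|
| 5% | 0.109 | 0.033 | 0 |
| 10% | 0.195 | 0.058 | 0 |
| 20% | 0.350 | 0.105 | 0 |

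This treats the scan estimate as a mean of epoch values. The plan averages spectra first, so it is an approximation.

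**4. In Hz.** This needs an epoch-level SD, which is an assumption. At 0.25, 0.5 and 1.0 Hz, the 10% upper bound (0.195 SD) is 0.049, 0.097 and 0.195 Hz. At ρ = 0.3 it is 0.015, 0.029 and 0.058 Hz.

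**5. Would a small bias matter?** Take a two-sided paired t-test at 5% with n = 120 × 0.9 = 108, as an illustration; the plan names no test. A systematic bias of b SDs of the paired difference gives noncentrality b√108. For b = 0.05, 0.1 and 0.2 (noncentrality 0.52, 1.04, 2.08) the false-positive rate is 8%, 18% and 54%. Steps 3 and 5 use different SDs, and neither is given, so they cannot be chained into one estimate.

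**6. Aim 2.** If the same constant c is added to each participant's pain-minus-baseline difference at both visits, corr(D₁ + c, D₂ + c) = corr(D₁, D₂). The test-retest correlation is unchanged. A uniform shift likewise leaves unchanged the correlation between pain and alpha on which Section 17 rests.

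**The case against.** The strongest reply is that this is silence in the plan and not a described bad practice. Much of that stands, and several stronger readings should be resisted.

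- *The cleaner sees the pain condition.* A reader might infer this. The documents say only nothing; masking is unspecified.
- *Segments are thrown away scan by scan.* Artifact removal is listed before epoching, and the method is not given. It could be cutting or correction, manual or automated.
- *The cleaner works with results in view.* Preliminary analyses are mentioned in the monitoring section, and the one defined outcome look comes after five data sets. Nothing says that the person cleaning sees either. Equally, nothing separates the roles.
- *Pain scans contain more movement.* They may, since participants rate pain during the scan. But Section 4 asks for stillness and uses the rating device in every scan, baseline included.
- *The shift is a known number of Hz.* Cleaning comes before the Fourier transform, so under the written order no epoch-level peak frequency exists when artifacts are removed. Perfect selection on one tail is therefore a ceiling.
- *The damage could never be found or undone.* If the recordings are kept, retained data can be counted and the scans cleaned again. What is lost is prespecification, because a rule chosen after results are known is open to the same doubt.

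It is also fair to say that renaming files would not by itself hide the condition. Section 4 describes the acute scan as five one-minute recordings (Section 9 lists it only as five minutes), and skin conductance, respiration and ECG are recorded alongside.

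None of this supplies a criterion or a masking step, so the gap remains.

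**Conclusion.** The point holds as a gap in Section 18: artifact removal rests on judgement, its method is unspecified, and no masking is planned, while the team has directional expectations and examines primary outcomes early. A biased Aim 1 difference requires two conditions together: removal must differ between pain and baseline scans, and it must be related to alpha frequency. The documents show neither to be true or false.

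The size and direction of any bias therefore cannot be stated. For 10% removal in one scan the range is 0 to about 0.2 epoch-level SD, with about 0.06 SD at a correlation of 0.3, assuming normal epoch values. The error rates in the working show only that a small systematic bias could matter at this sample size.

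A reader might also infer that Aim 2 reliability must suffer. That does not follow: a bias common to both visits leaves the test-retest correlation as it was.

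**What to change.** State in Section 18 that:

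- all scans are cut by script into equal one-minute pieces (15 epochs each), so that the acute scan cannot be recognised by its structure, and the pieces are given random codes;
- artifact removal is done on the EEG channels alone, without the pain ratings or the auxiliary channels;
- removal is finished and locked before condition and visit are revealed, including for the five data sets used in the interim look;
- the amount of data retained per scan is reported by condition.

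Add one sensitivity analysis that repeats the Aim 1 contrasts with an automatic amplitude-threshold rejection rule, its threshold fixed before unmasking.

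The cost is a cutting and coding script, cleaning in coded batches, and one extra analysis run. No additional staff are needed.
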